**CONFIDENTIAL**

Document Date: 29 Nov 2021

Page 13 of 34

ST-AD-008 version 05

## Statistical Analysis Plan

Sponsor Name: Golden Biotechnology Corporation  
Sponsor Protocol ID: GH Covid-2-001

Covance Study ID: 000000203201

Exclusion Criteria 12	patient requires frequent or prolonged use of systemic corticosteroids ( $\geq 20$ mg of prednisone/day or equivalent for $>4$ weeks) or other immunosuppressive drugs (e.g., for organ transplantation or autoimmune conditions).	Non-Programmable check of the prior medications.
Treatment Compliance	patient with study treatment compliance $<50\%$	Non-Programmable check the study treatment compliance based on drug accountability data.
Prohibited Medication or Therapy	patient has used prohibited medications or therapies documented in the protocol or identified by clinical or medical team	Non-Programmable check of the concomitant medication data.

As defined in the table, all important protocol deviations leading to exclusion from the PPS will be determined non-programmatically from the data. Those criteria which require clinical or medical monitoring interpretation will be reviewed prior to database lock.

All important protocol deviations leading to exclusion from the PPS occurring during the study will be reviewed and approved by Golden Biotechnology Corporation prior to database lock and unblinding. Should additional important protocol deviations leading to exclusion from the PPS, not anticipated at the time of preparing this SAP, be identified during the study (and prior to unblinding) they will be documented in a SAP amendment/Per Protocol Set Identification Plan, other document and included in all relevant protocol deviation reviews and approvals.

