4.4.2. Hepatic injury or renal impairment

4.4.2.1. *Hepatic injury*

Discontinuation of study treatment for abnormal liver tests should be considered by the investigator when a patient meets one of the conditions outlined in [Figure 2](#) or if the investigator believes that it is in the best interest of the patient.

Figure 2: Stopping Criteria for Liver Injury

Abbreviations: ALT = alanine aminotransferase; INR = international normalized ratio; ULN = upper limit of normal
 Note: INR value is not applicable to patients on anticoagulants.

4.4.2.2. *Renal impairment*

If a patient has renal impairment (creatinine clearance <50 mL/min), treatment should be discontinued.

4.4.3. **Discontinuation of study treatment**

A patient may be discontinued early from study drug treatment (ET of study treatment) for the following reasons:

- Lack of efficacy (e.g. patients who require nonstudy antiviral or anticytokine therapy due to progression of COVID-19), and the investigator's decision. Note: remdesivir or other authorized treatments for COVID-19 is allowed if considered SoC, if started prior to randomization or during the study. Initiation of remdesivir or other authorized treatments for COVID-19 during the study will be considered a treatment failure if started due to progression of disease.
- Adverse event
- Withdrawal by patient (specify reason in the eCRF)
- Lost to follow-up
- Death

- Physician decision (i.e. investigator decision based on protocol deviation, assessment that it is not in the patient's best interest to continue, or other reason [specify reason in the eCRF]).
- Sponsor decision (specify reason in the electronic case report form [eCRF])

No temporary treatment discontinuation is permitted.

Patients who discontinue study treatment prematurely will be asked about the reason(s) for discontinuation and will be asked to continue all assessments up to Day 28. Patients will be educated about the continued scientific importance of their data and encouraged to complete the Day 28 Follow-up/EOS assessments even if they discontinue study treatment prematurely.

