6.2. Prohibited medications

Simultaneous participation in other clinical treatment study protocols is not allowed.

Treatment with any antiviral drugs (except remdesivir or other authorized treatments for COVID-19), or with any drugs known to be strong inhibitors or inducers of CYP2C19, 3A4, 2C8, and 2E1 are prohibited within 14 days or 5 half-lives prior to the start of study treatment. Drugs with a narrow therapeutic index that are substrates of 1A2, 2B6, 2C8, 2C9, 2C19, 3A, and 2D6 are also prohibited.

A list of commonly known CYP inducers and inhibitors is given in [Appendix 6](#) for reference use.

Antroquinonol is a purified compound from an extract of *A. camphorata*. For this reason, the use of *A. camphorata*-containing products is prohibited within 2 weeks prior to the first administration of study drug, and the use of *A. camphorata*-containing products other than antroquinonol is prohibited throughout the study.

Patients who begin to receive nonstudy antiviral medication after the start of study treatment will be discontinued from study treatment. Note: remdesivir or other authorized treatments for COVID-19 is allowed if considered SoC, if started prior to randomization or during the study. Initiation of remdesivir or other authorized treatments for COVID-19 during the study will be considered a treatment failure if started due to progression of disease.

Administration of an authorized COVID-19 vaccines is permitted as per the local health authority recommendation.

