CYP2C9	–	carbamazepine rifampin	aprepitant bosentan phenobarbital St. John's wort ^{2,3}
CYP2C19	–	rifampin	artemisinin
CYP3A	avasimibe ⁴ carbamazepine phenytoin rifampin St. John's wort ^{2,3}	bosentan efavirenz etravirine modafinil naftilin	amprenavir aprepitant armodafinil clobazamechinacea ³ pioglitazone prednisone rufinamide vemurafenib
CYP2D6	None known	None known	None known

Abbreviations: AUC = area under the curve; CYP = cytochrome P450 isoform.

NOTE: This is not an exhaustive list.

1. For a drug that is a substrate of CYP1A2, the evaluation of the effect of induction of CYP1A2 can be carried out by comparative pharmacokinetic studies in smokers vs. nonsmokers.
2. The effect of St. John's wort varies widely and is preparation-dependent.
3. Herbal product.
4. Not a marketed drug.

Source: Department of Health and Human Services, Food and Drug Administration. Guidance for Industry: Drug Interaction Studies - Study Design, Data Analysis, Implications for Dosing, and Labeling Recommendations. Draft, 2012.

Table 6: Examples of Sensitive In Vivo CYP Substrates and CYP Substrates with Narrow Therapeutic Range

CYP Enzymes	Sensitive substrates ¹	Substrates with narrow therapeutic range ²
CYP1A2	alosetron caffeine duloxetine melatonin ramelteon tacrine tizanidine	theophylline tizanidine
CYP2B6 ³	bupropion efavirenz	—
CYP2C8	repaglinide ⁴	paclitaxel
CYP2C9	celecoxib	warfarin phenytoin
CYP2C19	clobazam lansoprazole omeprazole	S-mephenytoin
CYP3A ⁵	alfentanil aprepitant budesonide buspirone conivaptan darifenacin darunavir dasatinib dronedarone eletriptan eplerenone everolimus felodipine indinavir fluticasone lopinavir lovastatin lurasidone maraviroc midazolam nisoldipine quetiapine saquinavir sildenafil simvastatin sirolimus tolvaptan tipranavir triazolam	alfentanil astemizole ⁶ cisapride ⁶ cyclosporine dihydroergotamine ergotamine fentanyl pimozide quinidine sirolimus tacrolimus terfenadine ⁶

CYP Enzymes	Sensitive substrates ¹	Substrates with narrow therapeutic range ²
	ticagrelor vardenafil	
CYP2D6	atomoxetine desipramine dextromethorphan metoprolol nebivolol perphenazine tolterodine venlafaxine	thioridazine pimozide

Abbreviations: AUC = area under the curve; CYP = cytochrome P450 isoform; OATP1B1 = organic anion transporting polypeptide 1B1; P-gp = P-glycoprotein 1.

NOTE: This is not an exhaustive list.

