### 2.3 Sample Size

A total of 174 patients are planned to be randomized into the study:

- 20 patients in the sentinel cohort (10 patients in each treatment group)
- 154 patients in the expansion cohort (77 patients in each treatment group).

This enrollment level ensures 80% power to demonstrate proof of concept efficacy with one-sided alpha of 0.2.

The sample size is based on the following assumptions:

- The randomized allocation ratio is 1:1 between the antroquinonol group and the placebo group
- The proportion of patients alive and free of respiratory failure is approximately 78% on placebo vs 89% on antroquinonol

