#### 5.4.1 Important Protocol Deviations Leading to Exclusion from the PPS Analysis

Only those important protocol deviations considered to have a major effect on efficacy will lead to complete exclusion of the patient from the PPS. For the purposes of this study, the following criteria have been identified as important protocol deviations leading to exclusion from the PPS as it is considered that the occurrences of any of these criteria might have an important influence on the primary efficacy endpoint. Patients will be assessed purely by comparison of their eCRF data with the criteria below.

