### 7.5.2 Prior and Concomitant Medications

Medications received prior to or concomitantly with study treatment will be coded using WHODrug Dictionary [Version Global B3 March 2020 (or a later version if updated during the study)].

Prior medications and concomitant medications are defined as follows:

Prior medications are those with a stop date prior to the first dose date of study treatment.

Concomitant medications are those with a start date on or after the first dose date of study treatment, or those with a start date before the first dose date of study treatment and a stop date on or after the first dose date of study treatment or ongoing end of study.

If a medication cannot be classified as "prior" or "concomitant" due to missing/incomplete dates, it will be classified as concomitant.

Prior medications and concomitant medications will be listed together and summarized separately for the ITT set.

The number and percentage of patients using each medication will be displayed together with the number and percentage of patients using at least one medication within each therapeutic class (ATC-Level 2) and generic term.

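### The per-protocol set drops patients for any prohibited drug at any time, including drugs started because of progression or after Day 14, and the check for two exclusion criteria misses ongoing use

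*SAP*

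**What the plan says.** SAP 5.4.1 lists the deviations that exclude a patient completely from the PPS. Its rationale is that "occurrences of any of these criteria might have an important influence on the primary efficacy endpoint", and it says patients are judged purely by comparing their eCRF data with the listed criteria. The Prohibited Medication or Therapy row reads: "patient has used prohibited medications or therapies documented in the protocol or identified by clinical or medical team". It is checked against the concomitant medication data. SAP 7.5.2 defines these as drugs started on or after first dose, or started earlier and continuing, with no last day.

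On what is prohibited:
- Protocol 6.2 says "Drugs with a narrow therapeutic index that are substrates of 1A2, 2B6, 2C8, 2C9, 2C19, 3A, and 2D6 are also prohibited", without a time limit.
- The same section takes patients who begin a nonstudy antiviral after the start of treatment off study drug. It exempts remdesivir and other authorized COVID-19 treatments given as standard of care.
- Protocol 4.4.3 gives as an example of lack of efficacy "patients who require nonstudy antiviral or anticytokine therapy due to progression of COVID-19".

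The SAP 5.4.1 rows for exclusion criteria 8 and 12 name prior medications as the data to check. SAP 7.5.2 states: "Prior medications are those with a stop date prior to the first dose date of study treatment".

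Under SAP 7.6, ITT is the primary efficacy population, and mITT and PPS are supportive.

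**The concern.** A per-protocol exclusion should depend on conduct that could alter the outcome, not on care given because of the outcome. This row does not separate the two. A patient who worsens, receives a nonstudy antiviral for that reason and goes on to respiratory failure is a primary-endpoint failure, and leaves the PPS because of treatment prompted by the worsening. A patient whose first prohibited drug is taken on Day 20 also leaves the Day 14 analysis, although that drug cannot meet the SAP's own rationale for exclusion.

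The opposite gap lies in the same table. Criterion 8 covers concurrent use, and criterion 12 covers frequent or prolonged corticosteroids or immunosuppressants, which are likely to be ongoing at entry. A drug still being taken at first dose is concomitant under SAP 7.5.2, so a check of prior medications does not find it.

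At stake is how the PPS can be read beside ITT. If membership depends partly on outcome, neither agreement nor disagreement between the two sets is clean evidence about robustness.

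**Working it through.** **Inputs from the documents.** SAP 2.3: "The proportion of patients alive and free of respiratory failure is approximately 78% on placebo vs 89% on antroquinonol"; 174 patients randomized 1:1, so 87 per arm. Protocol 8.1: 2% drop-out, so 174 × 0.98 / 2 = 85.26 evaluable per arm.

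**The plan's own figure.** SAP 2.3 states: "This enrollment level ensures 80% power to demonstrate proof of concept efficacy with one-sided alpha of 0.2". A simulation of the design (looks at 20, 80 and 174; stop at an odds ratio of at least 3.5, then 1.2, in favor of placebo; final one-sided Wald test at 0.2) gives 79.5% power at 87 per arm. The 80% is reproduced. The same comparison without futility looks has 87.0% power. The stated power is not in dispute.

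**Assumption not in the documents.** Let f be the share of an arm's failures removed by the row, varied from 0.25 to 0.75, with no successes removed.

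**Formulas.** With success rate p:
- PPS success rate = p / [p + (1 − p)(1 − f)]
- PPS odds ratio = true odds ratio × (1 − f placebo) / (1 − f active)
- True odds ratio = (0.89/0.11) / (0.78/0.22) = 2.28

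Expected failures: 85.26 × 0.22 + 85.26 × 0.11 = 18.8 + 9.4, about 28.

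**Equal removal in both arms**

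| f | Failures removed | Placebo | Active | Difference | Odds ratio |
|---|---|---|---|---|---|
| 0 | 0 | 78.0% | 89.0% | 11.0 | 2.28 |
| 0.25 | 7 | 0.78/0.945 = 82.5% | 0.89/0.9725 = 91.5% | 9.0 | 2.28 |
| 0.50 | 14 | 0.78/0.890 = 87.6% | 0.89/0.945 = 94.2% | 6.5 | 2.28 |
| 0.75 | 21 | 0.78/0.835 = 93.4% | 0.89/0.9175 = 97.0% | 3.6 | 2.28 |

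SAP 7.6.1 derives the risk difference from the control-group proportion and the odds ratio, so a raised PPS control rate shrinks the reported difference even though the odds ratio holds. In a fixed-design simulation at about 85 per arm, the chance of p < 0.2 goes from 86.2% to 80.8%, 71.8% and 56.9%.

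**Unequal removal**
- 60% of placebo and 40% of active failures: 2.28 × 0.4/0.6 = 1.52.
- 40% and 60%: 2.28 × 0.6/0.4 = 3.42.
- No drug effect (78% in both arms), 25% placebo and 50% active: 0.75/0.50 = 1.50, with a simulated one-sided rejection rate of 51% at the 0.2 level. The reverse gives 0.50/0.75 = 0.67 and 4%.

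**Criteria 8 and 12.** No arithmetic applies. Prior means stopped before first dose, and the check looks only at prior medications, so a drug ongoing at first dose lies outside it. Chronic prednisone illustrates this. The prohibited-medication row would not catch it either on the strong-inducer ban, because Protocol Appendix 6, Table 5 lists prednisone as a weak CYP3A inducer.

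**The case against.** A reader might infer that the row systematically strips primary-endpoint failures from the PPS. The documents do not support that.
- Remdesivir and other authorized treatments are exempt, so that rescue does not trigger the row. Protocol 6.2 names antivirals but not anticytokines, which would enter only if the clinical or medical team identified them.
- Progression is not the primary-endpoint event. A patient given a nonstudy antiviral for progression who never needs ventilation or high-flow oxygen, and survives, is a success. Excluding that patient removes a success, so the calculation above shows one direction only.
- It is tempting to add drugs used at intubation, because Table 6 in Protocol Appendix 6 includes "ergotamine fentanyl pimozide quinidine sirolimus tacrolimus". No section says these drugs are given at intubation. The point does not rest on that link.

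It can also be said that SAP 5.4 reserves exclusion for deviations with a major effect on efficacy, that criteria needing clinical interpretation are reviewed before lock, and that exclusions are approved before unblinding. This stands in part. But SAP 5.4.1 presents the listed rows as those deviations and judges patients purely against them. Blinded review prevents selection by arm, not selection by outcome.

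On criteria 8 and 12, concurrent nonstudy antivirals and the immunosuppressants in Table 6 (cyclosporine, sirolimus, tacrolimus) can already be caught by the prohibited-medication row. The gap is therefore narrower than all ongoing use. It also assumes that prior in the table has its SAP 7.5.2 meaning.

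Finally, neither ITT nor mITT uses this row, and no stated success criterion or DMC rule depends on the PPS. That limits the consequence.

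**Conclusion.** The concern holds for the supportive PPS. The row has no time limit, covers drugs that the protocol links to progression, and excludes patients from the Day 14 analysis for drugs that cannot affect it. How much this matters depends on shares that the documents do not give, so the 25% to 75% range and the 60/40 splits are illustrations, not predictions. Equal removal of failures compresses the risk difference but leaves the odds ratio unchanged; only unequal removal biases the odds ratio. It would be wrong to infer that the primary ITT result is biased or that the trial's power is misstated. The gap for criteria 8 and 12 is real but smaller: the named check misses some ongoing use at entry. Both should be settled before database lock.

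**What to change.** In SAP 5.4.1:
- Count prohibited-medication use, including drugs ongoing at first dose, only if it occurs before the earlier of the analysis day (Day 14 for the primary endpoint, Day 28 for Day 28 endpoints) and the first date of respiratory failure or death. Counting use rather than new starts matters: exclusion criterion 14 has no row of its own, and a limit to drugs started after first dose would miss patients already on a prohibited drug at entry.
- State that treatment started because of COVID-19 progression, or given for or after respiratory failure, does not by itself exclude a patient from the PPS.
- For exclusion criteria 8 and 12, change the identification method to a check of prior and concomitant medications, covering drugs started before and ongoing at first dose.

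The cost is SAP wording. Protocol 6.1 already collects medication dates and reason for use, Protocol 7.1.2.6 the start date of respiratory intervention, and Protocol 7.1.2.4 mortality. The downsides are a slightly larger PPS that keeps some exposed patients, and membership that may differ between Day 14 and Day 28 analyses. No change to which drugs are prohibited is proposed.

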### 5.5 Safety Set (SS)

All patients who have received at least 1 dose of the study treatment. Patients will be analyzed according to the study treatment they actually received.

### 5.6 Pharmacokinetic Set (PKS)

Patients in the sentinel cohort who have received at least 1 dose of the study treatment and have at least 1 evaluable plasma concentration without important protocol deviations or events thought to significantly affect the PK.

## 6. DATA Handling

### 6.1 Time points and Visit Windows

Day 1 is defined as the day of first dose of study treatment. Relative days on or after Day 1 are calculated as (target date – Day 1 date) + 1. Relative days prior to Day 1 are calculated as (target date – Day 1 date). The day prior to Day 1 is Day -1.

The following visit windows will be used for by-visit analyses.

## Statistical Analysis Plan

Sponsor Name: Golden Biotechnology Corporation

Sponsor Protocol ID: GH Covid-2-001

Covance Study ID: 000000203201

Visit	Target Day of Visit a	Acceptable visit window
Day 3	Day 3	Days 2 to 3
Day 5	Day 5	Days 4 to 6
Day 7	Day 7	Days 7 to 8
Day 14 - EOT	Day 14	Days 14 to 16
Day 28 - Follow up	Day 28	Days 26 to 30

a relative to the date of first dose of study treatment.

For all populations, multiple visits within the same window will be dealt with as follows:

- If both scheduled and unscheduled visits fall within the same visit window, the scheduled visit will be used for analysis.
- If multiple scheduled visits occur within a single visit window, then the visit closest to the target day of the visit window will be used in the analysis. If there is a tie, the later visit will be used in the analysis.
- If multiple unscheduled visits occur within a single visit window (with no scheduled visit within the window) then the unscheduled visit closest to the target day of the visit window will be used in the analysis. If there is a tie, the later unscheduled visit will be used in the analysis.

Baseline value is defined as the last scheduled or unscheduled value collected prior to the first dose of study treatment. Assessments carried out on day of first study treatment administration are considered to have taken place before the study treatment administration, if the corresponding times have not been recorded.

## 6.2 Handling of Dropouts, Missing Data, and Outliers

Unless specified otherwise, no imputation for missing/partial dates will be performed for missing safety, efficacy, PK variables. For time-to-event efficacy variables, the censoring rules for no event data will be included in efficacy analysis section.

For patients with clinical improvement score above 2 or missing at discharge, missing scores on the next day after discharge will be imputed to 2. After above rule implemented, missing scores will be imputed using Last Observation Carried Forward for a maximum of 1 day at Day 7, 2 days at Day 14, and 4 days at Day 28.

Dates in original form will be used in all listings.

No rules for outlier detection are planned.

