4.1. Inclusion Criteria

Patients must satisfy all of the following criteria at the screening visit unless otherwise stated:

1. Willing and able to provide informed consent.
2. Male or female patients between 18 and 80 years of age.
3. Oxygen saturation <94% in room air at screening.
4. Hospitalized with mild COVID-19 disease (not requiring oxygen therapy [WHO COVID-19 Clinical Improvement Ordinal Scale, score of 3] or requiring oxygen therapy by mask or nasal prong [WHO COVID-19 Clinical Improvement Ordinal Scale, score of 4]). Requirement of oxygen therapy by mask with reservoir to treat severe COVID-19 pneumonia is not allowed for enrollment.
Note: Hospitalized patients can also include patients admitted to centers conditioned as hospitals to treat COVID-19 patients.
5. Chest x-ray or CT scan consistent with pneumonia.
6. Onset of COVID-19 symptoms within 2 weeks prior to randomization.
7. SARS-CoV-2 infection confirmed by a PCR test, antigen, or any authorized commercial or public health assay (nasopharyngeal, oropharyngeal, or respiratory samples, not serology testing).
8. Male patients and female patients of childbearing potential must agree to use protocol-specified methods of contraception ([Appendix 4](#)).
9. Female patients of childbearing potential must have a negative pregnancy test at screening or pretreatment on Day 1.
10. Male patients must agree not to donate sperm from the first dose through 90 days after the last dose of study treatment; female patients of childbearing potential should refrain from donation of ova from Day 1 until 90 days after the last dose of study treatment.
11. Patient is, in the opinion of the investigator, willing and able to comply with the study treatment regimen and all other study requirements.

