8.3. General Considerations

Continuous variables will be summarized by the standard descriptive statistics: number of patients (n), mean, standard deviation, median, minimum, and maximum. Frequency of patients or events and percentages will be summarized in categorical variables.

Missing values on clinical improvement score will be imputed using Last Observation Carried Forward for a maximum of 1 day at Day 7, 2 days at Day 14, and 4 days at Day 28. For

respiratory failure status, where a patient has died, their status will not be considered missing but will be treated as an observation at each timepoint.

Unless otherwise stated, all regression models will be adjusted for age and remdesivir or other authorized treatments for COVID-19 use at baseline.

Results will be considered statistically significant at one-sided alpha of 0.025, and considered to indicate promising trend at one-sided alpha of 0.2.

Additional information is available in the statistical analysis plan (SAP).

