- h Efficacy parameter assessments: [1] Confirmation of whether the patient is discharged to home, is in the hospital, or has worsened to require an ICU. The number of days a patient has been hospitalized prior to study entry will be recorded in the eCRF. [2] PCR testing for SARS-CoV-2 will be performed by a local or central laboratory at screening. Results of confirmatory COVID-19 test already done as standard of care can be used to determine eligibility. All subsequent tests will be performed by a central laboratory at baseline/Day 1, Day 5 (+/-1 day) and Day 14 (+2 days). Also at Follow-up/EOS if patient is hospitalized. Either nasopharyngeal or mid-turbinate samples are allowed for central testing. Only one method should be used throughout the study for the participant. [3] Clinical improvement score will be measured using the WHO COVID-19 Clinical Improvement Ordinal Scale (refer to [Appendix 7](#)). [4] Patient mortality will be recorded up to Day 28. Every effort will be made to ascertain vital status in all randomized patients (eg, with a vital records search) up to Day 28. [5] Respiratory failure is considered as patient need for invasive mechanical ventilation, non-invasive ventilation, high-flow oxygen, or ECMO. The date of the start of the respiratory intervention must be recorded in the eCRF; no daily assessment is needed. [6] COVID-19 symptoms (presence or absence of dry cough, dyspnea (shortness of breath/ difficulty in breathing), or chills/rigors, myalgia (muscle pain), headache, sore throat, and loss of taste or smell; other symptoms that could be related to COVID-19) will also be assessed during hospitalization, on discharge, ET/EOT and Follow-up/EOS visit (at the site, home visit, or via telephone or telemedicine if patient has been discharged).

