Appendix 7. World Health Organization COVID-19 Clinical Improvement Ordinal Scale

A special World Health Organization committee arrived at an ordinal scale (given in the [table below](#)) that measures COVID-19 illness severity over time.

Patient State	Descriptor	Score
Uninfected	No clinical or virological evidence of infection	0
Ambulatory	No limitation of activities	1
	Limitation of activities	2
Hospitalized Mild disease	Hospitalized, no oxygen therapy	3
	Oxygen by mask or nasal prongs	4
Hospitalized Severe Disease	Non-invasive ventilation or high-flow oxygen	5
	Intubation and mechanical ventilation	6
	Ventilation + additional organ support – pressors, RRT, ECMO	7
Dead	Death	8

Abbreviations: ECMO = extracorporeal membrane oxygenation; RRT = renal replacement therapy.

Source: World Health Organization. WHO R&D Blueprint. Novel Coronavirus COVID-19 Therapeutic Trial Synopsis. Draft February 18, 2020.

Summary of Amended Protocol Changes

A Phase 2 Randomized, Double-blind, Placebo-controlled, Proof of Concept Study to Evaluate the Safety and Efficacy of Antroquinonol in Hospitalized Patients with Mild to Moderate Pneumonia due to COVID-19

Protocol Version 4.0 Date: 09 July 2021, Status: Final

Protocol Version 3.1 Date: 29 March 2021

Protocol Version 3.0 Date: 11 March 2021

Protocol Version 2.0 Date: 02 September 2020 (submitted to FDA)

Protocol Version 1.1 Date: 01 June 2020 (submitted to FDA)

Original Protocol Version 1.0 Date: 14 May 2020 (submitted to FDA)

Investigational Product: Antroquinonol (Hocena®)

Protocol Reference Number: GH Covid-2-001

Investigational New Drug: 149841

Sponsor:

Golden Biotechnology Corporation
[name]
[name]

Sponsor Signatory:

[name]
VP, Clinical Medicine Research Department
Golden Biotechnology Corporation
[name]
[name]

Medical Monitor:

[name]
Senior Medical Director
LabCorp Drug Development
E-mail: [contact]
[contact]

Information described herein is confidential and may be disclosed only with the express written permission of the Sponsor.

Document History

Protocol Version	Date	Reason for version change
Protocol Version 4.0	08 July 2021	This version was updated to address feedback from Data Monitoring Committee (DMC) and Investigators.

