## 8. Changes in Planned Analysis

No changes on statistical analysis methods from the protocol.

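### SAP 6.2 imputes a WHO score of 2 after any recorded discharge, without limiting the rule to discharge home or excluding scores 5-7, so a departure on respiratory support could count as improvement in secondary endpoints

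*SAP*

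**What the plan says.** SAP 6.2 has two steps for a missing WHO score. The first is: "For patients with clinical improvement score above 2 or missing at discharge, missing scores on the next day after discharge will be imputed to 2". The second applies afterwards: "missing scores will be imputed using Last Observation Carried Forward for a maximum of 1 day at Day 7, 2 days at Day 14", with a limit of 4 days at Day 28.

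Protocol 8.3 has only the second step: "Missing values on clinical improvement score will be imputed using Last Observation Carried Forward for a maximum of 1 day at Day 7", with the same limits at Days 14 and 28. SAP section 8 nevertheless says: "No changes on statistical analysis methods from the protocol".

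On the scale in Protocol Appendix 7, score 2 is an ambulatory grade ("limitation of activities"). Scores 3 and 4 are hospitalized mild disease. Score 5 is "Non-invasive ventilation or high-flow oxygen", score 6 is intubation with mechanical ventilation, and score 7 adds other organ support. Eligible patients start at 3 or 4 (Protocol 4.1).

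SAP 7.6.2.1 uses the score in an ordinal regression at Days 7, 14 and 28, and in Cox models for time to 2-point improvement, time to score 2 or lower, and time to score 0.

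Neither document defines discharge or mentions transfer to another facility. The setting item in Protocol Appendix 5 reads: "Confirmation of whether the patient is discharged to home, is in the hospital, or has worsened to require an ICU".

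**The concern.** The rule is sensible for the patient it seems to be meant for, someone sent home from score 3 or 4 who was not scored the next day. But it is written for every score above 2, which includes 5, 6 and 7, and for a missing score whatever came before it. It asks neither where the patient went nor why.

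If someone on non-invasive ventilation leaves and the site records a discharge, the analysis reads that departure as improvement. So a deterioration can become a favorable event in the time-to-event endpoints. The same patient may count as a respiratory failure in the primary analysis.

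The missing-score limb needs no transfer at all. A patient last scored 5 who leaves with no discharge score is also set to 2. SAP 7.6.2.2 takes the opposite line for hospital and ICU duration, where an unknown discharge date is treated as continued stay to Day 28.

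**Working it through.** The plan gives no figure for this rule, so there is none to reproduce. The check is a trace of the rule, followed by an illustration of size.

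**1. When the rule applies.** Three things are needed: a recorded discharge, a discharge score above 2 or missing, and no score the next day. The score is scheduled on Days 1, 3, 5, 7, 14 and 28 and at discharge (Protocol Appendix 5), besides screening. The next-day score will therefore usually be missing. A recorded next-day score is never overwritten.

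**2. Trace of a patient with score 5, 6, 7 or missing at a recorded discharge on Day d.** The score on Day d + 1 becomes 2.

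| Endpoint | Baseline 4 | Baseline 3 |
|---|---|---|
| Time to score 2 or lower | event | event |
| Time to 2-point improvement | event (4 - 2 = 2) | no event (3 - 2 = 1) |
| Time to score 0 | no event | no event |

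Two features of SAP 7.6.2.1 may block the false event. Its first censoring rule censors at the start of an authorized COVID-19 treatment not prescribed at baseline, which a deteriorating patient may already have received. Both rules also censor at Day 28 a patient who has died by then. The exposed patients are mainly survivors, under the second rule or with no such new treatment.

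**3. Reach into the ordinal regression.** Suppose the score at visit day V is missing and the carry-forward limit is L days, counted to the target day. The imputed 2 reaches V if 0 ≤ V - (d + 1) ≤ L.

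- Day 7, L = 1: d = 5 or 6.
- Day 14, L = 2: d = 11 to 13.
- Day 28, L = 4: d = 23 to 27.

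An earlier discharge is stopped by the limit.

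**4. Comparison with the protocol rule.** Under Protocol 8.3 alone, a discharge score of 6 is carried forward as 6 within the limits. Under SAP 6.2 it becomes 2. That is a change of method.

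**5. Illustrative count.** The documents give no rate of departure on support. Assume that a share f of the design's Day 14 failures leaves this way with no next-day score. The design has 22% failures on placebo and 11% on antroquinonol (Protocol 8.1) and 174 / 2 = 87 per arm. False events for score 2 or lower are 87 × 0.22 × f and 87 × 0.11 × f.

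| f | Placebo | Antroquinonol |
|---|---|---|
| 5% | 1.0 | 0.5 |
| 10% | 1.9 | 1.0 |
| 25% | 4.8 | 2.4 |
| 50% | 9.6 | 4.8 |

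**6. Illustrative hazard ratios.** All inputs here are assumed: 87 per arm, exponential recovery with mean 10 days on placebo, and a hazard ratio of 1.4 among patients who do not leave on support. Departures fall on Days 3-12, all recorded as discharges, with those patients truly unrecovered to Day 28.

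| Departures, placebo vs drug | Coded unrecovered | Coded by the rule | Shift in log HR |
|---|---|---|---|
| 6% vs 3% | 1.42 | 1.37 | ln(1.37/1.42) = -0.04 |
| 10% vs 5% | 1.45 | 1.35 | ln(1.35/1.45) = -0.07 |
| 3% vs 6% | 1.18 | 1.37 | ln(1.37/1.18) = +0.15 |

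Repeat runs differ by up to about 0.04 in the hazard ratio. The standard error of the log hazard ratio at this size is about 0.16, so the first two shifts are under half a standard error and the third is nearly one.

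**The case against.** A reader might infer that any ventilated patient who is transferred out is counted as recovered. The documents do not support that.

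- The rule is triggered by discharge, not by transfer, and neither document says that a transfer is recorded as a discharge. SAP 2.2 describes discharge of patients considered ready for it, who then take capsules at home. The setting item separates home from hospital and ICU, so a patient moved to another hospital could properly be recorded as still in hospital.
- The note in Protocol 4.1 that "Hospitalized patients can also include patients admitted to centers conditioned as hospitals to treat COVID-19 patients" treats those centers as hospitals. It does not say that worsening patients leave them by transfer.
- Recovered is too broad a word. Time to score 0 is never affected, and 2-point improvement is affected only from baseline 4.
- The primary endpoint is untouched, because respiratory failure status is collected separately. Mortality and the Day 7 and Day 28 respiratory-failure analyses would still show harm.
- Protocol 8.3 refers to the SAP for further detail, and Protocol 8.4 bases the efficacy analysis on the final SAP. The undeclared change is therefore a small matter.

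All of this stands, and it limits how often the rule can misfire. It does not alter the text, which has no upper score limit, no destination condition and no definition of discharge. Relying on sites to record every such departure as still in hospital is an assumption that the SAP should replace with a rule.

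**Conclusion.** The concern holds as a gap in a stated imputation rule. Read literally, SAP 6.2 scores a recorded discharge on score 5-7 support, or a missing discharge score after a last score of 5-7, as 2 the next day when no score exists for that day. It could therefore create false events for time to score 2 or lower and, from baseline 4, for 2-point improvement. It could also place a 2 in the ordinal regression for the discharge days shown above.

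The size cannot be fixed from the documents. At low shares it is one or two patients per arm. It becomes material only if such departures are common or clearly unequal between arms. With equal shares under the design alternative, the false events fall more on placebo and work against antroquinonol. If the drug were harmful, they would favor it. A general claim that the rule favors the drug, or that it hides harm, is not supported. The hazard ratios above depend entirely on assumed departure rates.

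The mismatch between Protocol 8.3, SAP 6.2 and SAP section 8 stands however rare these departures are. Sample size, power and the primary analysis are unaffected.

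**What to change.** In SAP 6.2:

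- Impute 2 only when the setting recorded at discharge is outpatient/home and the discharge score is 3 or 4. If the discharge score is missing, use the last in-hospital score.
- For any other departure, do not impute 2 and do not count the departure as an improvement event. Carry the last observed score forward only within the existing 1, 2 and 4 day limits. Keep the patient at risk until an observed score shows improvement or the existing censoring applies.
- If the patient is recorded as discharged home, the last score is 5-7 and the discharge score is missing, leave the score missing beyond those limits. Run a sensitivity analysis with 2 imputed.

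An open-ended carry-forward of the last score should be avoided. It would break the limits in both documents and could code a patient at home as still hospitalized.

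In SAP section 8, list the discharge rule as a change from Protocol 8.3.

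The cost is a few sentences, one programming condition and one sensitivity run. Setting and score are already scheduled at the discharge visit, so no new data or patients are needed. The change should be made before unblinding.
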